### 3.1 STATISTICAL ANALYSIS PLAN

Prior to conducting formal analyses baseline demographic characteristics and key clinical measures will be compared between the women in the two treatment arms using contingency table approaches for categorical variables and analysis of variance models and t-tests for continuous variables. For all of these analyses, comparisons will be made within Global Network site and overall across the sites controlling for site in the models.

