## **7.2 Adjustments for Covariates**

As this is a randomized trial and the randomization process was not compromised during execution, the treatment effect estimate from trial is unbiased, even without adjusting for any baseline covariates. Therefore, no adjustments for covariates other than site are planned for the primary analysis. However, baseline clinical and demographic variables that are known predictors of neonatal mortality and maternal outcomes will be included in secondary analyses of intervention efficacy.

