### **8.4 Demographic and Baseline Characteristics**

Demographic and baseline clinical characteristics for the study participants will be summarized by treatment group using the general analysis rules describe above for the mITT, ITT, PP and SAF populations. Variables of interest include maternal age, maternal education, gravidity, maternal weight and BMI, previous pregnancy loss, number of antenatal care visits, delivery attendant, delivery location, and type of delivery.

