## 9.4 Primary Analysis

The primary analysis will compare the risk of preterm birth between the two treatment arms using two complementary approaches. First, the formal test of the primary hypothesis that the risk of preterm birth differs between the two arms will utilize a modified intention-to-treat approach based on a Cochran-Mantel-Haenszel test stratified by Global Network sites. The approach is characterized as a modified intention to treat approach because the analysis population for the test will be all randomized pregnancies for which the delivery occurs after 20 weeks. Earlier deliveries (miscarriages) will be considered missing completely at random for purposes of this analysis.

In order to evaluate the sensitivity of the primary hypothesis test to the assumption by which miscarriages are treated as randomly missing and to control for potential confounders of the treatment effect, additional analyses will be conducted using a series of three generalized linear models. These generalized linear models will be fit with the binary outcome of preterm (<37-week delivery) as the outcome measure. The initial model will include terms for treatment, site, and a treatment by site interaction. If the treatment by site interaction term is found to be significant ( $p<0.05$ ), then all subsequent models will include the interaction term and all effects will also be reported by site, although formal inference will be based on the average effect across sites. If the interaction term is not significant, it will be removed from the model and this initial model be used to estimate an unadjusted treatment effect controlling for site. The second series of models will include any demographic or clinical variable found to differ significantly between the treatment arms in the preliminary analyses described above. These models will be used to generate adjusted estimates of the treatment effect controlling for potential confounders. The third set of models will utilize extensions of the generalized linear model that incorporate inverse probability weighting to evaluate the sensitivity of the inference to treatment of miscarriages as randomly missing (Hogan, 2004). As described in Section 7.3, we will also conduct sensitivity analyses using the full ITT population; for these analyses, missing data due to loss to follow-up will be handled using multiple imputation, and these early terminations will be treated as preterm deliveries.

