### **9.6 Analyses of Other Outcomes of Interest**

In addition to these planned formal primary and secondary outcome analyses, we will also conduct exploratory outcomes for a number of other binary outcomes. The analytic approach for these exploratory analyses, will be comparable to that planned for the primary and secondary analyses but will focus on estimation of effect sizes and generation of hypotheses, therefore the analytic approach will be comparable to the effect estimation approach described for the primary analysis. Initially, contingency tables will be used to generate estimates of the risk of each outcome for the two treatment arms, both overall and separately by Global Network (GN) site and across all sites, and the relative risk associated with treatment will be estimated by site and across sites controlling for site. For each outcome a series of generalized linear models analogous to those described for the primary outcome will be used to generate unadjusted estimates of risk, estimates of risk adjusted for potential confounders, and estimates of risk adjusted to account for any possible differences in risk between the arms associated with miscarriages.

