## **12. CHANGES TO THE ANALYSES PLANNED IN THE PROTOCOL**

Additional sensitivity analyses beyond those included in the original protocol have been included in Sections 7.3 and 9 to account for loss-to-follow-up and to account for early pregnancy losses. Also, one secondary outcome variable has been modified and one secondary outcome variable has been added. The outcome of risk of preeclampsia or eclampsia has been modified to clarify that this outcome is the risk of a hypertensive disorder of pregnancy. This modification was made to clarify the true variable of interest, reflecting the data collection process used in the MNH registry. The outcome of preterm, preeclampsia has been added to the secondary outcome list to reflect additional research that was reported on this outcome after the study was launched.

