#### **14. ATTACHMENTS**

Table 1	Participant Distribution
Table 2	Baseline Characteristics
Table 3	Patient Medication Compliance
Table 4	Reasons for Noncompliance
Table 5	Primary and Secondary Efficacy Outcomes
Table 6	Key Safety (SAE) Outcomes
Table 7	Protocol Deviations
Figure 1	Consort Diagram

Table 1. Participant Distribution

GN Site	Screened N	Consented N (%)	Eligible N (%)	Randomized N (%)	Analysis Population Membership N (%)				Withdrew consent N (%)	Study Terminations - N (%)		
					Safety	MITT	ITT	PP		Terminated	Participant moved away from study area	Investigator terminated participant
GN02: DRC												
GN03: Zambia												
GN06: Guatemala												
GN08: India (Belagavi)												
GN09: Pakistan												
GN11: India (Nagpur)												
GN12: Kenya												
Total												

NOTE: Analysis population membership % will be out of randomized.

Table 2: Baseline Characteristics – For ITT and MITT Populations

Variable	Placebo	Aspirin	Total
Randomized, N			
Maternal Age, N (%)			
< 20			
20-29			
> 29			
Median (P25, P75)			
Projected GA at Enrollment, N (%)			
6,0 - 7,6			
8,0 - 9,6			
10,0 - 10,6			
11,0-11,6			
12,0 - 13,6			
Median (P25, P75)			
Maternal Education, N (%)			
No formal			
Primary			
Secondary			
University+			
Maternal Height			
Mean (StdDev)			
Median (Min, Max)			
Maternal Weight			
Mean (StdDev)			
Median (Min, Max)			
BMI			

Variable	Placebo	Aspirin	Total
Mean (StdDev)			
Median (Min, Max)			
Number of Antenatal Care Visits			
Median (P25, P75)			
Delivery Attendant, N (%)			
Physician			
Nurse/Nurse midwife			
TBA			
Family/Self/Other			
Delivery Location, N (%)			
Hospital			
Clinic/Health Center			
Home/Other			
Delivery Mode, N (%)			
Vaginal			
C-Section			
Miscarriage			
MTP			

Table 3: Participant Medication Exposure and Compliance – For MITT and ITT Populations

Compliance/Exposure Parameter	Placebo (N = XXXX)	Aspirin (N = XXXX)
No Drug		
Gestational age at first dose (weeks)		
Mean (StdDev)		
Median (Min, Max)		
Gestational age at last dose (weeks)		
Mean (Std Err)		
Min, Max		
Total number of days doses taken		
Mean (Std Err)		
Min, Max		
Level of Adherence: N (%)		
0% – 30%		
30% – 50%		
50% – 70%		
70% – 90%		
>90%		
Level of Exposure: N (%)		
0% – 30%		
30% – 50%		
50% – 70%		
70% – 90%		
>90%		

*NOTE: Summaries of gestational age at first and last dose excludes individuals who never initiated treatment while such individuals are included in summaries of all other parameters.*

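### SAP 9.4 and 9.5 choose adjustment covariates by an undescribed between-arm significance screen that conflicts with SAP 7.2, and the only variable lists class four post-randomisation variables as baseline

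*Combined protocol and SAP*

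**What the plan says.** **The selection rule.** SAP 9.4 (primary outcome) and SAP 9.5 (secondary outcomes) state that the second series of generalised linear models will "include any demographic or clinical variable found to differ significantly between the treatment arms in the preliminary analyses described above". SAP 9.6 contains no screen of its own. It plans models analogous to those for the primary outcome, to give among other things "estimates of risk adjusted for potential confounders".

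**Where the rule comes from.** The sentence is carried over from protocol 3.1.1 and 3.1.2. There it points back to protocol 3.1, under which "baseline demographic characteristics and key clinical measures will be compared between the women in the two treatment arms" by contingency tables, analysis of variance and t-tests. Protocol 3.1 names no variables and no threshold. SAP 12 opens its list of changes with "Additional sensitivity analyses beyond those included in the original protocol have been included in Sections 7.3 and 9" and records no change to the covariate rule.

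**The other rule.** SAP 7.2 adjusts the primary analysis for site only and adds that "baseline clinical and demographic variables that are known predictors of neonatal mortality and maternal outcomes will be included in secondary analyses". It names no variables.

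**The lists.** SAP 8.4, on demographic and baseline characteristics, ends its list with "number of antenatal care visits, delivery attendant, delivery location, and type of delivery". Shell Table 2, headed as baseline characteristics, has rows for "Number of Antenatal Care Visits", delivery attendant, delivery location and "Delivery Mode, N" (%). The categories under that last row are vaginal, C-section, miscarriage and MTP.

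**The concern.** A significance screen between randomised arms picks out chance imbalances, real effects of treatment, or both. For a variable fixed before randomisation only chance can operate. The screen is then a weak way to choose covariates and leaves the model unspecified until the data are seen, but it does not bias the estimate.

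A variable measured after randomisation is different. It can differ between arms because treatment changed it, or because treatment changed the outcome. A woman who delivers early has fewer weeks in which to attend antenatal care, so an effect on preterm birth itself creates a difference in visit counts. The screen then tends to select the variable when treatment works, and adjustment removes part of the effect.

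Two things are at stake. Analysts have two different rules for the same supportive models. And the lists they would most naturally turn to mix pre- and post-randomisation variables under one baseline label.

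**Working it through.** **1. Is the screen described in the SAP?** SAP 7.1 gives descriptive statistics. SAP 8.4 says characteristics are summarised. Table 2 has no p-value column. SAP 7.5 allows for p-values on baseline characteristics but calls them descriptive and names no test. So the SAP neither describes the comparison nor states a threshold for it, and 7.5 fits poorly with using those p-values to build models.

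**2. Do the two rules agree?** No. SAP 7.2 selects on prognosis, whatever the imbalance; 9.4 and 9.5 select on imbalance, whatever the prognosis. The prognosis in 7.2 concerns neonatal mortality and maternal outcomes, and preterm birth is not mentioned. SAP 9.4 cites 7.3 but not 7.2; 9.5 and 9.6 cite neither.

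**3. What is on the lists?** Each has ten variables. SAP 8.4 has gravidity and previous pregnancy loss, where Table 2 has gestational age at enrolment and height. The same four in each are post-randomisation: antenatal visits, delivery attendant, delivery location, delivery type or mode. No time point is given for the visit count, but a total accrues after enrolment at 6 0/7 to 13 6/7 weeks.

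**4. Chance selection.** At an assumed 0.05 per variable with no true differences, at least one of the four passes with probability 5% if they are fully correlated, and 1 - 0.95^4 = 18.5% if independent.

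**5. Preterm birth, visit count as the example.** From the documents: 5,483 per arm and 8.0% v 6.4% (true RR 0.80). Assumed:
- gestational age at preterm delivery = 37 minus an exponential with mean 2.5 weeks, floored at 20; at term, normal (39.3, SD 1.2), floored at 37
- visits = round((GA - 12)/k + normal error), floored at 0
- screen = t-test at p < 0.05; model = Poisson log-link with treatment and visits; 2,000 simulated trials per row

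| k (weeks between visits) | Error SD | Passes screen | RR in selected trials, unadjusted → adjusted | Rule-average RR |
|---|---|---|---|---|
| 2 (about 14 visits by term) | 1 | 32.6% | 0.770 → 0.850 | 0.824 |
| 2 | 2 | 15.2% | 0.777 → 0.823 | 0.806 |
| 3 (about 9) | 1 | 20.0% | 0.775 → 0.836 | 0.811 |
| 3 | 2 | 10.7% | 0.786 → 0.811 | 0.803 |
| 4 (about 7) | 1 | 13.5% | 0.778 → 0.820 | 0.807 |
| 4 | 2 | 8.0% | 0.792 → 0.809 | 0.804 |
| 5 (about 5) | 1 | 10.9% | 0.780 → 0.812 | 0.804 |
| 5 | 2 | 7.5% | 0.794 → 0.804 | 0.799 |

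With a true RR of 1.0 (SD 1; k = 2, 3, 5) the rule average is 1.000, 0.997 and 0.998. For scale, SE(log RR) = sqrt(0.92/(5,483 × 0.08) + 0.936/(5,483 × 0.064)) = 0.069, so the 95% CI around 0.80 is 0.70 to 0.92. Within selected trials, the mean absolute error against 0.80 is about the same adjusted or unadjusted, except at k = 2, SD 1 (0.078 v 0.047) and, less so, at k = 3, SD 1 (0.055 v 0.044).

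**6. Pregnancy-loss outcomes, delivery mode.** SAP 9.2 defines late abortion, spontaneous abortion and MTP largely from the registry's mode-of-delivery item, which appears to be the source of the Table 2 row. Within its miscarriage category the risk of miscarriage is essentially 100% in both arms, and elsewhere 0%. The adjusted RR is therefore about 1 or not estimable, whatever the true RR.

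How often would delivery mode pass an assumed 0.05 screen? Take 5,960 per arm, a four-category chi-square on 3 df (critical value 7.815), and MTP assumed at 1% in both arms. Any change in miscarriage is spread in proportion over caesarean and vaginal delivery. Let d be the between-arm difference in miscarriage, m the mean miscarriage proportion, and r the mean proportion delivering vaginally or by caesarean. The noncentrality is λ = (5,960 d²/2)(1/m + 1/r). At 5% miscarriage (protocol 3.2) and RR 0.80: d = 0.010, m = 0.045, r = 0.945, so λ = 0.298 × (22.22 + 1.06) = 6.94 and the pass rate is 0.585.

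| Miscarriage RR (5% on placebo) | λ | Passes screen |
|---|---|---|
| 1.00 | 0 | 5% |
| 0.95 | 0.40 | 7.5% |
| 0.90 | 1.65 | 16% |
| 0.80 | 6.94 | about 58% |

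SAP 7.3 expects 2% to 8% total loss before 20 weeks, miscarriage and MTP together. Taking out the assumed 1% MTP leaves 1% to 7% miscarriage. At RR 0.80, λ then runs from 1.34 to 9.90 and the pass rate from about 14% to 76%.

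**The case against.** No text makes 8.4 or Table 2 the candidate list for the screen. The protocol sentence behind the rule speaks of baseline characteristics, SAP 7.2 speaks of baseline variables, and 9.4-9.6 justify adjustment by confounding, which a delivery variable cannot cause in a randomised comparison. A careful statistician would leave the four out. All of this stands, and it is why the exposure is a possibility left open by a label, not a planned error. It does not close the gap. The SAP itself labels the four as baseline, the rule admits any demographic or clinical variable, and no other list exists.

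The practical effect is also limited. For preterm birth the distortion is small and every visit schedule above is assumed. The pregnancy-loss outcomes are exploratory. The documents give no effect of aspirin on miscarriage: 0.80 is the design effect for preterm birth, so the 58% is one point on a wide range. A model that adjusts miscarriage for itself would probably fail visibly. These points stand too.

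A reader might infer that the main result is at risk. The documents do not support that: the formal test is the site-stratified Cochran-Mantel-Haenszel test, SAP 7.2 allows no covariate but site in the primary analysis, and the note to Table 5a keeps the adjusted RR out of the primary paper. Nor can one infer that the screen biases estimates when only true baseline variables are eligible. There the objection is one of prespecification and efficiency.

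**Conclusion.** The concern holds in a limited form, and its priority is minor. SAP 9.4 and 9.5 rest on preliminary analyses that the SAP does not describe, give no threshold, and state a different rule from 7.2. The only variable lists class four post-randomisation variables as baseline and disagree with each other.

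If one of the four entered a model, only the supportive adjusted estimates would suffer. For preterm birth the average shift is from 0.80 to at most about 0.82, with none under no effect; this rests on assumed visit schedules and a 0.05 screen. For miscarriage, late abortion and MTP, adjusting for delivery mode would make the adjusted RR uninformative. How often the screen would bring that about depends on an unknown effect on miscarriage: 5% of trials with no effect, and about 58% at RR 0.80 with 5% miscarriage.

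The documents do not support saying that the SAP plans to adjust for delivery variables, because the link from 8.4 and Table 2 to the screen is an inference. Table 5a has a column for the adjusted RR, but the documents do not say where it will be published.

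**What to change.** - In SAP 9.4 and 9.5, replace the significance screen with a reference to 7.2. In 9.6, which has no screen to replace, add the same reference.
- In SAP 7.2, add predictors of preterm birth. Name there, before unmasking, the pre-randomisation covariates to be used whatever the imbalance: for example maternal age, gestational age at enrolment, BMI, education and prior pregnancy loss, with site.
- In SAP 8.4 and Table 2, move antenatal visits, delivery attendant, delivery location and delivery mode to a separate table of care and delivery after randomisation. State that they are not eligible as covariates, and make the two baseline lists agree.
- Record the change from protocol 3.1.1 and 3.1.2 in SAP 12.

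The cost is SAP wording and one table shell. The example covariates are already in 8.4 or Table 2, so no new data are needed. The primary test and the site-adjusted estimate do not change.

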## 9.5 Secondary Outcome Analyses

This study has been designed to evaluate the differences between the two treatment arms for three secondary outcomes: the risk of perinatal mortality; the risk of eclampsia/preeclampsia, and the risk of a SGA delivery. As with the primary analyses, each of these outcomes will be examined individually using descriptive tests of hypotheses that the risk differs between the two arms based on Cochran-Mantel-Haenszel tests stratified by Global Network sites. The analyses for each of these 3 secondary outcomes will utilize the same modified intention-to-treat population used for the primary outcome. Each of these hypothesis tests will be conducted at the 0.05 level of significance with no adjustment for multiple comparisons. In addition to this set of hypothesis tests, model-based analyses comparable to those conducted for the primary analyses will be used to evaluate potential heterogeneity of treatment effect across sites and evaluate potential confounding. For each of the 3 outcomes, an initial model will include terms for treatment, site, and a treatment by site interaction. If the treatment by site interaction term is found to be significant ( $p<0.05$ ), then all subsequent models will include the interaction term and all effects will be reported by site; because the study will lack power to detect site-specific effects, all p-values will be reported for the average effect and site effects will include point and interval estimates. If the interaction term is not significant, it will be removed from the model and this initial model be used to estimate an unadjusted treatment effect controlling for site. The second series of models will include any demographic or clinical variable found to differ significantly between the treatment arms in the preliminary analyses described above. These models

will be used to generate adjusted estimates of the treatment effect controlling for potential confounders.

### **9.6 Analyses of Other Outcomes of Interest**

In addition to these planned formal primary and secondary outcome analyses, we will also conduct exploratory outcomes for a number of other binary outcomes. The analytic approach for these exploratory analyses, will be comparable to that planned for the primary and secondary analyses but will focus on estimation of effect sizes and generation of hypotheses, therefore the analytic approach will be comparable to the effect estimation approach described for the primary analysis. Initially, contingency tables will be used to generate estimates of the risk of each outcome for the two treatment arms, both overall and separately by Global Network (GN) site and across all sites, and the relative risk associated with treatment will be estimated by site and across sites controlling for site. For each outcome a series of generalized linear models analogous to those described for the primary outcome will be used to generate unadjusted estimates of risk, estimates of risk adjusted for potential confounders, and estimates of risk adjusted to account for any possible differences in risk between the arms associated with miscarriages.

### **10. SAFETY ANALYSIS:**

No formal safety analyses are planned as a part of this study, although rates of pregnancy complications identified by ultrasound will be summarized as will SAEs and hospitalizations. No formal hypothesis tests will be conducted, but descriptive p-values generated using Cochran-Mantel-Haenszel statistics with stratification by GN site will be generated.

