## ABSTRACT

---

**Background:** Preterm birth (PTB) remains the leading cause of neonatal mortality and long term disability throughout the world. Though complex in its origins, a growing body of evidence suggests that first trimester administration of low dose aspirin (LDA) holds promise to reduce the rate of PTB substantially.

**Hypothesis:** First trimester administration of aspirin will reduce the risk of preterm birth.

**Study Design Type:** Prospective randomized, placebo-controlled, double-blinded multicenter clinical trial. Trial will be individually randomized with one-to-one ratio (intervention/control)

**Population:** Nulliparous women between the ages of 18 and 40, with a singleton pregnancy between 6 0/7 weeks and 13 6/7 weeks gestational age (GA) confirmed by ultrasound prior to enrollment, no more than two previous first trimester pregnancy losses, and no contraindications to aspirin. Minors who are  $\geq$  14 years of age may be enrolled if permitted by the country's ethical guidelines.

**Intervention:** Daily administration of low dose (81 mg) aspirin [also known as acetylsalicylic acid (ASA)], initiated between 6 0/7 weeks and 13 6/7 weeks GA and continued to 36 0/7 weeks GA, compared to an identical appearing placebo. Compliance and outcomes will be assessed biweekly.

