#### 2.2.2 Exclusion Criteria

- Women prescribed daily aspirin for more than 7 days;
- Multiple gestations;
- Fetal anomaly by ultrasound (Note most fetal anomalies are not detectable by ultrasounds done at this early gestation. Subsequent discovery of a fetal anomaly is not viewed as an exclusion.);
- Hemoglobin  $< 7.0$  g/dl at screening;
- Systolic blood pressure  $\geq 140$  and diastolic  $\geq 90$  at screening;
- Any other medical conditions that may be considered a contraindication per the judgment of the site investigator (e.g., Lupus, Type 1 Diabetes, or any other known significant disease)

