2) **Data Monitoring Committee (DMC)**: The DMC, a standing group that monitors all NICHD-funded Global Network studies, will be responsible for ensuring safe and ethical treatment of study participants through monitoring of the study. The membership will include, at a minimum, a statistician, obstetrician, pediatrician and an expert in international health. The DMC designated by NICHD will review the data collected at approximate 6 month intervals throughout the course of the study. The DMC reports, which are prepared by the Data coordinating center, will include information on study enrollment rates and participant progress through the study, participant compliance with protocol-specified treatment regimens, protocol violations, adverse events, and efficacy outcomes. The focus of the DMC review will be on monitoring participant safety and study progress/futility but data on treatment effectiveness will also be presented to frame the DMC discussions on safety and futility. However, no formal interim analysis of efficacy or effectiveness are planned and the DMC will not be responsible for stopping the trial for efficacy. The DMC will be charged with monitoring adverse events and side effects from LDA. All known associated side effects and specific obstetric or fetal concerns will be considered reportable to the DMC. The study will be reviewed by the DMC bi-annually at a minimum, but may be reviewed more frequently if concerns are raised about participant safety or about adequate process of the study.

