### **3.7.4 Ultrasound Gestational Age Dating**

All study sonographers will be trained to assess gestational age using CRL measurements. A sample of ultrasound images at each site will be reviewed by study investigators to ensure that CRL is accurately measured and gestational age is accurately assigned. If discrepancies are found, the sonographers will be retrained. Ultrasound will be used only for pregnancy dating and no other purpose.

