## 4 DATA FORMS

The following forms will be used for this study:

Form Description	Purpose	Key Data Elements	Data Source
Screening Log	To track screening and enrollment at facility or community level	Contact information, screening and enrollment date and status	Patient report
Initial Screening and Recruitment	To determine eligibility and record consent status	Screening criteria: age, pregnancy history, estimated GA by LMP, consent status/date.	Patient report, obstetrical wheel,
Ultrasound Screening	To confirm eligibility criteria by ultrasound.	GA dating, assessment of fetal anomaly, singleton pregnancy, and fetal heart rate	Ultrasound
Hemoglobin (Hb) Monitoring	To monitor Hb at enrollment and 26-30 GA. It will also capture Hb at 4 weeks post-randomization in subset of 500 women	Hemoglobin	Lab test
Clinical Assessment	To assess clinical status through examination and patient history and provide information on medicine distribution/use	Height, weight, BP, Pulse, patient-reported medical history, use of other medications	Clinical exam, lab tests, patient report
Biweekly Monitoring	To monitor side effects, use of other medications, and drug compliance.	Drug compliance, BP, side effects (nausea, vomiting, rash/hives, diarrhea, vaginal bleeding, gastritis, other), use of other medicines, care seeking, pregnancy complications.	Pill count, patient report, clinical examination
Blood Pressure Monitoring	To monitor BP for active identification of pre-eclampsia	BP, urine protein (if indicated), fetal movement, diagnosis of eclampsia or stroke.	Clinical examination, patient report
Unscheduled Emergency Visit	To monitor unscheduled medical visits or medical emergencies	Patient status, pulse, BP, reason for medical visit/emergency, pill count and patient report on drug compliance, presence of side effects, referrals	Existing medical records, patient reports
Severe Adverse Events	To record fatal, life-threatening, or any other serious, unexpected adverse event	Date/time of event, date/time of resolution, nature of adverse event, management of adverse event, attribution to study (yes/no).	Patient reports, existing medical records
Study Withdrawal	To describe reasons for study termination or withdrawal	Date and reason for termination/withdrawal.	Patient report
Protocol Deviation	To record protocol deviations and corrective actions	Date and nature of deviation/violation, corrective action.	Patient report, study records

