# APPENDIX 1. SCHEDULE OF STUDY PROCEDURES

	6 0/7- 13 6/7 weeks GA	Randomization /Enrollment	Bi-weekly after enrollment	4 weeks after enrollment	monthly after enrollment	16-20 weeks GA	26-30 weeks GA	34 weeks GA	36 weeks GA until delivery	6 weeks Post-Partum	As needed
Screening											
• Initial eligibility	X										
• Ultrasound	X										
Consent	X										
Clinical Assessments											
• Physical exam		X									
• Medical history		X									
• Use of other medicines		X	X								
• Maternal Hb monitoring		X		X			X				
• BP Monitoring		X				X	X	X	X		
Medication Activities											
• Instructions for drug use		X									
• Medication compliance			X								
• Resupply					X						
Outcome Assessment											
• Preterm Birth										X	
• SGA										X	
• Preeclampsia/ Eclampsia			X							X	X
• Other maternal outcomes			X							X	X
• Other fetal outcomes										X	X
• Unanticipated medical care											X
• Serious Adverse Events											X

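### SAP 10 plans no by-arm summary of five prompted on-treatment side effects, while its ultrasound item has no scheduled source after randomisation

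*Combined protocol and SAP*

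**What the plan says.** SAP 10 states that no formal safety analysis is planned, but that "rates of pregnancy complications identified by ultrasound will be summarized as will SAEs and hospitalizations", and that "descriptive p-values generated using Cochran-Mantel-Haenszel statistics with stratification by GN site will be generated". The shell for safety results, Table 6, is a serious adverse event table whose denominator is the safety population. It has no row for ultrasound findings or for non-serious symptoms.

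The protocol's list of data forms (section 4) shows what is collected on treatment. The Biweekly Monitoring form records "side effects (nausea, vomiting, rash/hives, diarrhea, vaginal bleeding, gastritis, other), use of other medicines, care seeking, pregnancy complications". Protocol 2.4.5 has staff meet each woman every two weeks to monitor side effects, until 36 0/7 weeks or delivery.

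On ultrasound, the abstract has gestational age "confirmed by ultrasound prior to enrollment", and Appendix 1 has a single ultrasound entry, in the column headed "6 0/7- 13 6/7 weeks GA", ahead of the randomisation column. Protocol 3.7.4 says "Ultrasound will be used only for pregnancy dating and no other purpose". Among the exclusions in protocol 2.2.2 is "Fetal anomaly by ultrasound (Note most fetal anomalies are not detectable by ultrasounds done at this early gestation"; the same entry goes on to say that an anomaly found later is not an exclusion.

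**The concern.** Safety is a central aim of this protocol. Section 2.8 notes that earlier work had not assessed aspirin in pregnancy in developing countries, and it heads its first safety strand with active surveillance of maternal side effects. The trial pays for that surveillance at every biweekly visit, yet the analysis plan never turns most of it into a comparison between arms.

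At stake is the tolerability result. The protocol presents low dose aspirin as a safe, widely available intervention for nulliparous women who are otherwise largely healthy, so readers will want symptom rates to set against any benefit. The same data help to explain adherence. SAP 8.2 removes from the adherence denominator any period when a woman was told to stop because of a side effect, so readers would see that adjustment without the rates behind it. Meanwhile SAP 10 gives a between-arm p-value to an ultrasound item whose source and timing it does not define.

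**Working it through.** The plan states no figure on this point, so the check sets collection beside analysis and then adds two small counts.

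**1. Biweekly form items (protocol section 4) against planned analyses (SAP 9.2, SAP 10, table shells)**

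| Item on the form | In SAP 10 | Elsewhere in the SAP |
|---|---|---|
| Nausea | no | no |
| Vomiting | no | no |
| Rash/hives | no | no |
| Diarrhea | no | no |
| Gastritis | no | no |
| Other | no | no |
| Vaginal bleeding | no | yes: SAP 9.2 (form ASP06, Question 2e), Table 5a |

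Six symptoms are named. One is analysed, so 6 − 1 = 5 are not, and 'other' is also left without a summary.

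**2. Could another table fill the gap?** Table 4 lists feeling sick from the pills as a reason for noncompliance. It counts only visits at which pills were not taken as instructed, so it misses women who had symptoms and carried on. It also uses the mITT population, which leaves out women whose pregnancy ended before 20 weeks. It is not a side-effect rate.

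**3. Is the omission declared?** Change in maternal hemoglobin is expressly moved to a separate plan (SAP 3.3 and 4.3). The prompted side effects receive no such statement. SAP 2 allows further exploratory analyses but commits to none of these.

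**4. How much is collected?** Visits on treatment = (36 0/7 weeks − gestational age at entry) ÷ 2 weeks.
- Latest entry: 36 weeks 0 days − 13 weeks 6 days = 22 weeks 1 day, or about 11 visits.
- Earliest entry: 36 − 6 = 30 weeks, or 15 visits.

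Women who deliver before 36 0/7 weeks have fewer. The planned enrolment is 11,920.

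**5. Where could ultrasound findings come from?**
- Scheduled study scans: one (Appendix 1). Scheduled after randomisation: none.
- Listed ultrasound forms: one, for screening. It records gestational age, anomaly, singleton status and fetal heart rate.
- Abnormal results at that scan: an anomaly or multiple gestation is an exclusion (protocol 2.2.2), and a live singleton with a heartbeat is an inclusion requirement (2.2.1).
- Later findings: protocol 2.8 says that abnormalities or losses discovered at ultrasound procedures or follow-up visits are noted. No later scan or dedicated form is listed.

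From the scheduled scan, an arm comparison would describe the state before treatment in women already screened for those findings. From any later scan, it would depend on who happened to be scanned in local care.

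**The case against.** Several points on the other side are fair, and they limit what can be said.

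A reader might infer that the ultrasound item is empty by design, or that aspirin could not have affected it. The documents do not support that. SAP 10 does not say that it means the screening scan, and protocol 2.2.2 and 2.8 both foresee later discoveries. What stands is that source and timing are unspecified and ascertainment is not uniform. The dating-only sentence in protocol 3.7.4 adds little, because the eligibility criteria and the screening form use the same scan for heartbeat, singleton status and anomaly.

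A reader might also infer that upper GI bleeding is lost unless it happens to be serious. It is not: protocol 3.5.1 makes every occurrence trigger the SAE form, and Table 6 has a row for it. Fetal anomaly, gastroschisis and antepartum and postpartum hemorrhage are handled in the same way.

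The text under the first strand of protocol 2.8 lists unplanned medical visits, hemoglobin, iron, hemorrhage, cesarean delivery and hemorrhage death, and names none of the five symptoms. Much of that content is analysed. The support for a symptom summary therefore comes from the strand's heading, protocol 2.4.5 and the form itself, which is enough.

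Finally, protocol 3.5.3 says that "The DMC will be charged with monitoring adverse events and side effects from LDA". That covers oversight during the trial. It does not put a tolerability result into the final report.

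**Conclusion.** The point holds in a limited form. Five named side effects and 'other', prompted for at about 11 to 15 visits in women treated to 36 0/7 weeks, have no planned by-arm summary in SAP 10 or in any table shell. The ultrasound item in SAP 10 needs a stated source and timing, because no study scan is scheduled after randomisation.

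The safety report is not otherwise empty: SAEs, hospitalizations, hemorrhage, maternal mortality and vaginal bleeding are covered. The primary efficacy analysis is untouched. This is an improvement the plan should make, not a flaw that threatens its main conclusion.

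The conclusion rests on the text, Appendix 1 and the table shells. The flowchart and the study schematic are not available in the copy reviewed. It also assumes that the biweekly form was used as the protocol's form list describes.

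**What to change.** In SAP 10 add, for the safety population, the number and percentage of women reporting each of nausea, vomiting, rash/hives, diarrhea, gastritis and 'other' at any biweekly visit, by arm, with the site-stratified CMH descriptive p-value already planned. SAP 9.2 already uses a yes-at-any-visit rule for vaginal bleeding from this form, and the same rule can be applied. Put the results in a new table. Table 6 is the SAE summary and should not mix serious events with prompted non-serious symptoms from another form.

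Restrict the ultrasound item to findings first recorded after randomisation, name the form they come from, and label them as incidentally ascertained.

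The cost is SAP wording and one table from data already collected. SAP 7.6 already foresees an addendum, and SAP 4.4 places unmasking after data lock, so the change can be made while masked. The downside is six more descriptive p-values. With no true differences, about 6 × 0.05 = 0.3 of them would be expected below 0.05 by chance, so the table should carry the descriptive-only wording of SAP 7.5.
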